Subsequent dose levels will enroll patients based on 3+3 design, whereby 3 patients will be initially enrolled and treated at each dose level. If one of these 3 patients experiences a DLT during the initial 28-day evaluation period, the dose level will be expanded to 6 patients. The MTD will have been exceeded if $\geq 33\%$ of patients experience DLT at a given dose level. DLT will have occurred when a patient has 1 or more toxicity listed in

[Table 6](#) that is at least possibly related to TRC253 during the first 28 days of dosing. Patients who exit the study for reasons other than DLT prior to completion of the 28-day DLT evaluation period will be replaced to ensure an adequate safety assessment in each cohort. Patients who experience DLT who receive less than the prescribed dose of TRC253 due to documented toxicity during the DLT evaluation period will be considered evaluable for dose escalation purposes. At the MTD or MED, up to twelve patients may be enrolled prior to confirming the RP2D. Dose escalation will take into account all

available data including PK/PD data and the safety profile of prior cohorts, as evaluated by medical monitor and Principal Investigators.

While the maximum tolerated dose was not reached, PK exposures at the 320 mg dose level significantly exceeded the target efficacious concentration and a decision was made not to proceed to 400 mg. Based on review of PK and safety, the RP2D of 280 mg was chosen.

Part 2 will consist of three cohorts of initially up to 15 patients (Cohort 1), up to 30 patients (Cohort 2), and up to 15 patients (Cohort 3) to receive TRC253 at the RP2D of 280 mg. The objective of Part 2 is to gather additional information on the safety, PK and PD characteristics, and the clinical efficacy of TRC253 in a pre-defined population of patients with metastatic CRPC. Patients enrolled into Part 2 will have received prior treatment with enzalutamide or apalutamide. Patients will be centrally screened for the presence of the AR F877L and AR L702H mutations from a plasma sample and enrolled into Cohort 1 (AR F877L positive), Cohort 2 (patients without AR F877L and without sole AR L702H mutations), or Cohort 3 (sole AR L702H mutation positive).

Treatment will continue until one or more of the withdrawal criterion are met; refer to [Section 7.4.3](#).

Patient Population:

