12. Major surgery (e.g., requiring general anesthesia) within 3 weeks before screening, or has not fully recovered from prior surgery (i.e., unhealed wound), or surgery planned during the time the patient is expected to participate in the study. **Note:** patients with planned surgical procedures to be conducted under local anesthesia may participate.
13. Plan to father a child while enrolled in this study or within 90 days after the last dose of study drug.
14. Pre-existing chronic hypokalemia or hypomagnesemia.

NOTE: Investigators should ensure that all study enrollment criteria have been met at screening. If a patient's status changes (including laboratory results or receipt of additional medical records) after screening but before the first dose of study drug is given such that he no longer meets all eligibility criteria, supportive treatment may be administered, if necessary, so that eligibility criteria can be met and laboratory test(s) may be repeated once, to determine if the patient qualifies for the study. If enrollment criteria are not met after further evaluation, then the patient should be excluded from participation in the study.

Dosage and Administration

Part 1: a single dose of TRC253 will be taken on the first day (i.e., Cycle 1 Day 1) of a 7-day cycle. During Cycle 1, the pharmacokinetic characteristics of a single dose of TRC253 will be investigated.

TRC253 will be administered orally once daily in the morning in 28-day cycles starting in Cycle 2. Starting with treatment Cycle 2 Day 1, TRC253 will be taken once daily in the morning. The proposed TRC253 doses are 40 mg, 80 mg, 160 mg, 240 mg, 320 mg, and 400 mg; however, intermediate dose levels may be implemented based on safety, tolerability, PK, PD and other observations at each dose level following review of data with the principal investigators at all treating sites.

Part 2: TRC253 capsules are taken once daily in the morning starting on Cycle 1 Day 1 at the MTD or MED in 28-day cycles.

On extended PK days, no food should be consumed for at least 8 hours before and 4 hours following TRC253 dosing. On all other days, no food should be consumed for at least 2 hours before and 1 hour after dosing.

Withdrawal Criteria:

Patients will be withdrawn from study treatment if, in the opinion of the Investigator, it is medically necessary, or if it is the wish of the patient. In addition, patients will be withdrawn from treatment for any of the following reasons:

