6.1.4. Treatment Period

Laboratory tests do not need to be repeated at cycle 1 day 1 if they were completed within 7 days prior in screening.

Part 1 Cycle 1

Patients will receive a single dose of TRC253 on Cycle 1 Day 1 for PK studies. No food should be consumed for at least 8 hours before and 4 hours after the TRC253 dosing. Blood pressure and heart rate will be measured prior to dose administration and hourly (± 15 minutes) for the first 6 hours following the first dose of study drug administration on Cycle 1 Day 1.

To aid in selection of the RP2D, patients may undergo PET scans using FDHT, a radiopharmaceutical specifically designed to image binding to AR. In these patients, FDHT-PET scans will be obtained before initiation of therapy. Imaging will occur at 1 or more centers under their existing IND and institutional protocol.

Safety, PD, biomarker, and disease evaluations will be performed as specified in the Time and Events Schedule for Part 1 ([Table 7](#)).

Treatment Cycles

TRC253 capsules will be self-administered once daily in the morning from Cycle 1 Day 1 onwards (Cycle 2 Day 1 onwards for Part 1). On extended PK days, no food should be consumed for at least 8 hours before and 4 hours after the TRC253 dosing. On all other days, no food should be consumed for at least 2 hours before and 1 hour after dosing.

Safety, PK, PD, biomarker, and disease evaluations will be performed at the time points specified in the Schedules of Assessments ([Table 7](#) and [Table 8](#)).

Treatment will continue until one or more of the withdrawal criterion are met (refer to [Section 7.4.3](#)).

Part 1: Once the first expansion cohort reaches its primary endpoint, patients from the dose escalation phase of the study who continue to derive benefit from TRC253 treatment will be allowed to stay on treatment and will attend monthly visits, which are to occur a minimum of once every 4 weeks (± 2 days).

Part 2: Once the primary endpoint is reached in the expansion cohort, patients who continue to derive benefit from TRC253 treatment will be allowed to stay on treatment and will attend monthly visits, which are to occur a minimum of once every 4 weeks (± 2 days).

Study procedures to be performed at the monthly visits are specified in the Schedules of Assessments ([Table 8](#)).

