7.4.3. Patient Withdrawal Criteria

A patient will be withdrawn from the study for any of the following reasons:

1. Lost to follow-up or noncompliant

2. Withdrawal of consent
3. The sponsor terminates the study
4. Disease progression according to PCWG3 criteria ([Appendix 2](#), [Appendix 3](#))
 - a. Patients may continue on study drug if in the opinion of the Investigator, patient is deriving benefit from continuation of therapy. Continuation of therapy must be approved by the Sponsor.
5. Dose delay greater than 21 days
Note: In part 1, only patients who have received >75% of TRC253 doses during the DLT evaluation period will be considered evaluable. Patients who have received \leq 75% of TRC253 doses during the DLT evaluation period due to reasons other than toxicities, such as but not restricted to disease progression, missed appointments, non-compliance, and patient withdrawal, will be considered non-evaluable for DLT and will be replaced with a new patient.
6. Patients with AST or ALT elevations >5X ULN, or who meet Hy's Law criteria, i.e., concurrent elevation of AST or ALT >3X ULN and total bilirubin >2X ULN
7. Grade 4 adverse events
8. Patients who experience QTcF prolongation > 500 ms or > 60 ms change from baseline without electrolyte abnormalities and without response to TRC253 (See [Section 8.5.3](#))

If a patient discontinues study drug and withdraws from the study, the off-study visit assessments should be obtained.

If a patient is lost to follow-up, every reasonable effort must be made by the study-site personnel to contact the patient and determine the reason for discontinuation/withdrawal. The measures taken to follow up must be documented.

Study drug assigned to the withdrawn patient may not be assigned to another patient. Patients who withdraw for reasons other than toxicity will be replaced at the discretion of the sponsor.

If the patient withdraws consent, no further evaluation should be performed and no further attempt should be made to collect additional data. Data and samples that have already been collected will still be used as outlined in this study.

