8.5.2. TRC253 Dose Modification/Dose Interruptions

The phase 2 dose of TRC253 is 280 mg daily.

Dose modifications and/or dose interruptions may be warranted for patients who experience toxicities. Patients with toxicities that are manageable with supportive care (i.e., nausea or vomiting) may not warrant dose reduction. For any occurrence of grade 2 or greater non-hematologic toxicity, study drug may be held until toxicities have resolved or improved to grade 1 or baseline, then resume drug at the same dose if the event was a tolerable grade 2 (at PI's discretion). Dose interruption or reduction to 240 mg is also permitted for grade 2 toxicity at the discretion of the investigator. If the event is grade 3 or 4, the study drug dose should be reduced to 240 mg when resuming drug administration. For a subsequent episode of a grade 3 adverse event, dose reduction to 200 mg is warranted once patient has recovered. If there is no recovery to \leq grade 1 or baseline after a 21 day delay, the patient should be discontinued from the study.

Dose modifications or interruptions may be necessary for liver enzyme elevations. For grade 2 aspartate aminotransferase (AST) or alanine aminotransferase (ALT) elevation (>3 times to <5 times the upper limit of normal), without signs of severe liver damage, stop study drug until liver enzymes return to baseline values. Once liver enzymes have returned to baseline values, treatment may be reintroduced at 240 mg. Discontinue study drug for AST or ALT elevations $>5X$ ULN or for patients who meet Hy's Law criteria (concurrent elevation of AST or ALT $>3X$ ULN and total bilirubin $>2X$ ULN).

Dosage modification or treatment interruptions may also be necessary for patients with diarrhea or nausea/vomiting. Treat diarrhea at first signs with adequate hydration and antidiarrheal medication (e.g., loperamide), and consider treatment interruption if diarrhea continues. For grade ≥ 3 adverse events, first episode, patient should hold TRC253 until \leq grade 1 or baseline, then may restart at 240 mg. After a second episode of a grade 3 adverse event, further dose reduction to 200 mg is warranted once patient has recovered. If no recovery to \leq grade 1 or baseline after a 21 day delay, the patient should be discontinued from the study.

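### Sections 7.4.3 and 8.5.2 give opposite instructions for a recovered non-hematologic grade 4 event: withdraw the patient, or restart at 240 mg

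*Combined protocol and SAP*

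**What the plan says.** **Withdrawal side.** Section 7.4.3 opens: "A patient will be withdrawn from the study for any of the following reasons". Item 7 of its list reads, in full, "Grade 4 adverse events". The synopsis has the same item under the lead-in "patients will be withdrawn from treatment for any of the following reasons". The synopsis design text ("Treatment will continue until one or more of the withdrawal criterion are met; refer to" Section 7.4.3), Section 6.1.4 ("Treatment will continue until one or more of the withdrawal criterion are met", citing the same section) and the study-drug row of Table 8 all make 7.4.3 the rule that ends treatment.

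**Restart side.** Section 8.5.2 sets a hold-and-resume rule for non-hematologic toxicity of grade 2 or more, and then says: "If the event is grade 3 or 4, the study drug dose should be reduced to 240 mg when resuming drug administration". In the same section, the diarrhea paragraph and the nausea/vomiting paragraph each allow a restart at 240 mg after a first episode of grade 3 or higher. All three rules require recovery to grade 1 or baseline within 21 days. A further sentence asks Part 2 sites to consider dose reduction for Table 6 toxicities. Two hematologic rows of that table name grade 4 events.

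**Exceptions that are written out.** Item 4a of 7.4.3 covers progression: "Patients may continue on study drug if in the opinion of the Investigator, patient is deriving benefit". Item 8 limits QTcF withdrawal to patients "without electrolyte abnormalities and without response to TRC253" and points to Section 8.5.3. Item 7 has no exception and no pointer, and 8.5.2 does not mention 7.4.3.

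**The concern.** Both instructions cannot be followed for the same patient. If a non-hematologic grade 4 event resolves within 21 days, one section ends treatment and the other gives the dose at which to resume. The synopsis speaks of withdrawal from treatment and 7.4.3 of withdrawal from the study, but neither is compatible with resuming drug.

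The first stake is patient safety: whether someone is re-dosed after a grade 4 event would depend on which section the site opened. The second is the safety reporting. Section 14.4.1 summarizes adverse events that lead to stopping treatment. Section 14.4 and the safety paragraph of the synopsis also tabulate exposure duration and reasons for discontinuation. All three outputs differ according to whether the patient is withdrawn or continues at 240 mg.

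**Working it through.** The plan gives no figure to reproduce. The check is to apply both sections to the same event.

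| Event in a Part 2 patient on 280 mg | 7.4.3 and synopsis | 8.5.2 | Conflict? |
|---|---|---|---|
| Non-hematologic grade 4, recovered within 21 days | Withdraw (item 7) | Resume at 240 mg | Yes |
| First grade 4 diarrhea or nausea/vomiting, recovered within 21 days | Withdraw (item 7) | May restart at 240 mg | Yes |
| Either of these, not recovered at 21 days | Withdraw | Discontinue | No |
| AST or ALT above 5 times ULN | Withdraw (item 6) | Discontinue | No |
| Grade 3, recovered | Item 7 not met | Resume at 240 mg | No |
| Grade 4 neutropenia for more than 5 days, or grade 4 thrombocytopenia | Withdraw (item 7) | Consider dose reduction (Table 6 sentence); no separate hematologic rule | Withdrawal not stated; no express permission to resume |
| QTcF above 500 ms or more than 60 ms over baseline | Item 8, with its exception | Handled in 8.5.3 | Outside this point |

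The direct conflict is therefore confined to the first two rows: three restart rules in 8.5.2, of which one names grade 4 and two reach it through *grade 3 or higher*.

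**Where it bites.** Section 8.5.2 opens with the phase 2 dose of 280 mg and steps down to 240 mg and then 200 mg. A step down to 240 mg means nothing for Part 1 patients who started at 40 to 240 mg (1 + 1 + 2 + 6 = 10 of 22, Section 2.4). The problem is mainly in Part 2.

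**Size in the tables.** One affected patient moves a discontinuation percentage by 1/15 = 6.7 points in Cohort 1 or 3, 1/30 = 3.3 points in Cohort 2, and 1/60 = 1.7 points over Part 2, assuming full enrollment.

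**How much lies ahead.** Section 2.4 reports 12 patients in the expansion, of about 60 planned, so about 60 − 12 = 48 remained. It reports no grade 4 events. If that zero covers all 22 + 12 = 34 treated patients, and one rate applies across doses, the one-sided 95% upper bound on the rate is 1 − 0.05^(1/34) = 8.4%. That is about 0.084 × 48 = 4 patients. This is a bound and not a forecast.

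**The case against.** The strongest reply is that the documents already show which rule governs. The synopsis, Section 6.1.4 and Table 8 all run treatment until a 7.4.3 criterion is met. Section 8.5.2 can then be read as subordinate, setting a dose only if resumption is otherwise allowed. The second-episode sentences in 8.5.2 mention grade 3 alone, which suggests loose drafting and not a deliberate policy of re-dosing after grade 4. Much of this stands: a reader should not infer two stop rules of equal rank. But on the subordinate reading the reference to grade 4 in the general rule has no application. Section 8.5.2 also repeats the stop instructions for liver enzymes and for non-recovery, so someone using it alone would not learn that grade 4 means withdrawal.

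Two stronger readings are tempting and not supported:

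- **That the Table 6 sentence contradicts 7.4.3 as squarely as the restart rules do.** It only asks that dose reduction be considered, and grade 3 entries in that table raise no conflict. What stands is the omission: it does not say that grade 4 neutropenia or thrombocytopenia requires withdrawal.
- **That PSA response is compromised.** Section 14.8 reports an earlier PSA change for patients who stop before Week 12, and nothing in the documents gives a direction or size for any shift.

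It is also fair that no grade 4 event has been reported, so the risk is prospective. The event itself would still be counted among all adverse events and those of grade 3 or greater under either rule.

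**Conclusion.** The plan is wrong as written on this point. For a recovered non-hematologic grade 4 event, including first-episode diarrhea or nausea/vomiting, 7.4.3 and the synopsis require withdrawal while 8.5.2 provides for restart at 240 mg. The Table 6 sentence is a secondary gap.

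The consequence is possible re-dosing of a patient who should be withdrawn, with changes to three safety outputs: events leading to discontinuation, reasons for discontinuation, and exposure duration. The documents do not show that this has happened, and no event rate is assumed. The conclusion rests on the text alone. It should be fixed, but it does not bear on sample size, schedule or the planned analyses.

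**What to change.** In 8.5.2, change *grade 3 or 4* to *grade 3* in the general rule, and *grade ≥3* to *grade 3* in the diarrhea and nausea/vomiting restart rules. Add a sentence on these lines: *patients with a grade 4 adverse event are withdrawn (Section 7.4.3), except for QTcF prolongation, which is managed under Section 8.5.3.* Make the Table 6 sentence subject to it, and note the same QTcF exception in item 7 of 7.4.3 and of the synopsis list. The exception is needed because 8.5.3 allows re-challenge of some patients without a grade limit; an unqualified sentence would create a new conflict.

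If the sponsor intends resumption after some recovered grade 4 events, leave the 8.5.2 restart rules and write that exception into item 7 of 7.4.3 and the synopsis, citing 8.5.2. The choice is clinical and is the sponsor's to make.

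The cost is a text amendment with IRB approval. Section 17.1 exempts only purely administrative changes, and a restart rule affects patients.

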Nausea or vomiting should be treated with supportive care including anti-emetic therapy and, if persistent, may require treatment interruption or dose reduction. For grade ≥ 3 adverse events, first episode- patient should hold TRC253 until \leq grade 1 or baseline, then may restart at 240 mg. After a second episode of a grade 3 adverse event, dose further dose reduction to 200 mg is warranted once patient has recovered. If no recovery to \leq grade 1 or baseline after a 21 day delay, patient should be discontinued from the study.

Further dose reductions below 200 mg may be permitted following discussion with the Sponsor.

Additionally, in Part 2, patients should be considered for dose reduction if they experience toxicities outlined in [Table 6](#).

Dose interruptions are allowed for a maximum of 21 days; if dosing is not restarted in that time frame, the patient should be discontinued from the study.

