8.5.3. Management of QTcF Prolongation

If > 60 ms change from baseline occurs OR QTcF > 500 ms, TRC253 should be held and electrolytes evaluated and repleted (if required). Other possible etiologies should be investigated (e.g., cardiac ischemia), and telemetry monitoring initiated if indicated. Patients who experience QTcF prolongation > 500 ms or > 60 ms change from baseline without electrolyte abnormalities should permanently discontinue treatment except in patients who are responding to the drug, in whom a favorable benefit-risk exists per the Investigator and where the patient re-consents to continued treatment. Patients discontinued due to a > 60 ms change from baseline OR QTcF > 500 ms should also be monitored by a cardiologist, with a minimum of weekly QTcF assessments for at least two weeks and one QTcF assessment after four weeks.

If > 60 ms change from baseline occurs OR QTcF > 500 ms patients can be re-challenged at the same dose if there were electrolyte abnormalities present during the initial finding of QTcF prolongation, and after repleting electrolytes, the QTcF recovers to < 450 ms, and a favorable benefit-risk exists per the Investigator. Re-challenge patients should re-consent to continued treatment.

If there were no electrolyte abnormalities present initially during the finding of QTcF prolongation, but the patient is responding and a favorable benefit-risk exists per the Investigator patients should dose reduce to 240 mg and may resume treatment at this lower dose after recovery of the QTcF to < 450 ms. An additional dose reduction to 200 mg should be implemented for a subsequent >60 ms change from baseline or QTcF > 500 ms seen at the 240 mg dose level.

While ECG readings at the sites will be used for patient management purposes, an additional central read will be performed. Sites will receive clinical alerts for QTcF values > 500 ms and for > 60 ms changes from baseline as determined by the third-party vendor.

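### Section 8.5.2 names no lower resumption dose for a Part 2 patient already at 240 mg when his first Grade 3 event occurs

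*Combined protocol and SAP*

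**What the plan says.** Part 2 patients start at 280 mg daily. Section 8.5.2 then sets these steps.

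- First Grade 3 event, general rule: "If the event is grade 3 or 4, the study drug dose should be reduced to 240 mg when resuming drug administration". (Grade 4 events are a withdrawal criterion in Section 7.4.3, so Grade 3 is the case that matters here.)
- Next step, general rule: "For a subsequent episode of a grade 3 adverse event, dose reduction to 200 mg is warranted once patient has recovered".
- Diarrhea: after a first episode of Grade 3 or higher, the drug is held until recovery and a restart at 240 mg is permitted. Then: "After a second episode of a grade 3 adverse event, further dose reduction to 200 mg is warranted once patient has recovered". The nausea/vomiting paragraph follows the same pattern.
- Below that: "Further dose reductions below 200 mg may be permitted following discussion with the Sponsor".

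Two other sentences bring a patient to 240 mg without a Grade 3 event. For Grade 2 toxicity in general: "Dose interruption or reduction to 240 mg is also permitted for grade 2 toxicity at the discretion of the investigator". After a Grade 2 AST/ALT rise: "Once liver enzymes have returned to baseline values, treatment may be reintroduced at 240 mg".

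A further sentence says that "in Part 2, patients should be considered for dose reduction if they experience toxicities outlined in" Table 6. It names no dose.

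Section 8.5.3 handles QTcF separately. Patients with a qualifying prolongation "without electrolyte abnormalities should permanently discontinue treatment except in patients who are responding to the drug", subject to a favorable benefit-risk judgment and re-consent. Those responders drop to 240 mg, and a later qualifying event at 240 mg takes them to 200 mg.

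**The concern.** The steps in Section 8.5.2 appear to be written for a patient who is still at 280 mg. They count Grade 3 episodes and attach a fixed dose to each count; they do not refer to the dose the patient is taking. Yet the section itself creates patients who are at 240 mg with a Grade 3 count of zero. When such a patient has his first Grade 3 event, the only resumption dose named for him is the one on which the event occurred.

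What is at stake is the safety of a small group who have already needed one reduction. A site that follows the named dose would re-expose the patient to the same dose under a rule meant to lower it. A site that sees the gap has to improvise, and with approximately 20 centers in Part 2 the answers may differ.

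**Working it through.** This is a dosing rule, so there is no sample size, power or confidence interval to reproduce. The check is dose arithmetic followed by a rough count.

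**Step size under the written rule** (reduction = current dose − named resumption dose)

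- First Grade 3 event at 280 mg: 280 − 240 = 40 mg (40/280 = 14.3%).
- First Grade 3 event at 240 mg, if the named dose is used: 240 − 240 = 0 mg.
- Second Grade 3 event at 240 mg: 240 − 200 = 40 mg (40/240 = 16.7%).

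A patient whose first Grade 3 event came at 280 mg has one such event at 240 mg before moving to 200 mg. A patient who was already at 240 mg and restarts there has two.

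**Does the count include Grade 2 events?** The general rule refers to a later episode of a Grade 3 event, and the diarrhea and nausea/vomiting paragraphs number first and second episodes at that severity. A Grade 2 event does not start the count.

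**Section 8.5.3.** Most of it is unaffected. Discontinuation is the default without an electrolyte abnormality, same-dose re-challenge after electrolyte repletion is intended, and a repeat event at 240 mg already leads to 200 mg. The gap remains in one branch: a responder without electrolyte abnormality, already at 240 mg for another reason, who has his first qualifying QTcF event there.

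**How many patients?** The documents do not say. The inputs are the interim counts in the ongoing-results safety text of Section 2.4 (34 patients, 40 to 320 mg) and about 60 planned Part 2 patients.

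- Grade 2 QTcF: 3 of 34. The printed 6% does not fit, since 3/34 = 8.8%, but the count does: 17 + 3 + 2 = 22.
- Assume 240 mg is reached by 3/34, or by 5/34 if the two ungraded AST rises are added: 60 × 3/34 = 5.3; 60 × 5/34 = 8.8 patients.
- Related Grade 3 events outside QTcF: none is stated. Taking 0/34, the one-sided 95% upper limit is 1 − 0.05^(1/34) = 8.4%. Affected under 8.5.2: 5.3 × 0 = 0 up to 8.82 × 0.0843 = 0.74.
- With an assumed 20% rate of Grade 3 events of any cause: 8.82 × 0.20 = 1.8.
- The 8.5.3 branch, using 2/34 Grade 3 QTcF: 5.29 × 2/34 = 0.31 to 8.82 × 2/34 = 0.52, before the responder and electrolyte conditions reduce it.

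Section 2.5.1 reports one Grade 2 QTcF case (7%) and none of Grade 3 or higher in what appears to be a group of 15; the start of that text is not available. On that reading, 60 × 1/15 = 4 patients would reach 240 mg through QTcF, which is the same order, and the 8.5.3 figures would be too high for 280 mg.

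**The case against.** A reader might infer that the plan orders a 0 mg reduction for these patients. The general rule does not support that. A patient on 240 mg cannot be reduced to 240 mg, so that sentence is better read as silent about him. The literal same-dose result arises only in the diarrhea and nausea/vomiting paragraphs, and even there the restart is permitted, not required.

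The patient is also partly covered. Table 6 includes most non-hematologic toxicity of Grade 3 or above, so the sentence about considering a reduction points to him. Section 7.4.2 requires stopping treatment when safety or tolerability makes that best for the patient. AST/ALT above 5 times ULN, Hy's Law cases and Grade 4 events leave treatment altogether. This narrows the gap but does not close it, because none of these provisions gives a resumption dose.

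Counting Grade 3 episodes can be defended as a coherent scheme: 200 mg follows two Grade 3 episodes whatever the dose at the first. That is fair, but Section 8.5.3 already ties its 200 mg step to an event seen at 240 mg, so a link to current dose is the sponsor's own approach.

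The patient counts are weak, and that objection stands in full. Reduction for Grade 2 is discretionary, same-dose resumption after a tolerable Grade 2 event is allowed, the listed events (fatigue in 7 patients, for example) are not graded one by one, and the 20% rate is only an assumption. The range is not a bound in either direction.

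Finally, a blanket ban on resuming at or above the dose of the event would go too far. It would bind after unrelated Grade 3 events and for patients at 200 mg, where the plan leaves going lower to discussion with the sponsor.

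**Conclusion.** The point holds as a minor gap in a safety rule. For a Part 2 patient already at 240 mg, the general rule in Section 8.5.2 names no lower dose after a first Grade 3 event, and the diarrhea and nausea/vomiting rules allow restart at the same dose. The conclusion about the text rests on the wording alone and is firm.

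The size does not have the same standing: probably 0 to 2 patients of about 60, on assumptions that the documents cannot confirm. It would be wrong to infer a general failure of QTcF management, since Section 8.5.3 is affected in one branch only. It would also be wrong to infer any effect on the PSA response, rPFS or other planned analyses; no endpoint definition or statistical result changes.

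**What to change.** In Section 8.5.2, including the diarrhea and nausea/vomiting paragraphs, state that after a Grade 3 event at least possibly related to TRC253, and after recovery, the patient resumes one level below his current dose: 280 to 240 mg, or 240 to 200 mg. For a patient already at 200 mg, the dose is decided in discussion with the sponsor, as the section already provides for going below 200 mg.

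In Section 8.5.3, put the same step into the branch for a responder without electrolyte abnormality, so that a first qualifying QTcF event at 240 mg leads to 200 mg.

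Leave unchanged same-dose resumption after a tolerable Grade 2 event, same-dose re-challenge after electrolyte repletion, and every discontinuation rule.

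The cost is two or three sentences. No patients or visits are added, and the capsules in Section 8.1 make both doses (240 = 2 × 100 + 40; 200 = 2 × 100). The downside is that a few patients reach 200 mg one event earlier, a dose that was not a Part 1 level, although the plan already uses it as the second reduction.

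### Section 8.5.2 gives a 240 mg restart after a first Grade 4 non-hematologic event, while Section 7.4.3 item 7 withdraws every patient with a Grade 4 event

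*Combined protocol and SAP*

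**What the plan says.** **Withdrawal.** Section 7.4.3 opens its list with "A patient will be withdrawn from the study for any of the following reasons", and item 7 reads "Grade 4 adverse events". The synopsis carries the same item under a slightly different lead-in: "patients will be withdrawn from treatment for any of the following reasons". Item 7 has no limit by relatedness, type, duration or recovery. Two other items do carry exceptions. Item 4a, on progression, adds "Patients may continue on study drug if in the opinion of the Investigator, patient is deriving benefit from continuation of therapy", subject to sponsor approval. Item 8, on QTcF, spares patients who are responding. Section 6.1.4 and the drug-administration row of Table 8 both let dosing run until a 7.4.3 criterion is met.

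**Dose modification.** Section 8.5.2 starts from non-hematologic toxicity of Grade 2 or higher and then says "If the event is grade 3 or 4, the study drug dose should be reduced to 240 mg when resuming drug administration". The diarrhea paragraph, for Grade 3 or higher, has "adverse events, first episode, patient should hold TRC253 until" recovery, followed by an optional restart at 240 mg. The nausea/vomiting paragraph has the same rule: "adverse events, first episode- patient should hold TRC253 until" recovery, then 240 mg. For a repeat event the general rule says "For a subsequent episode of a grade 3 adverse event, dose reduction to 200 mg is warranted once patient has recovered"; the other two paragraphs also name Grade 3 only. A patient who has not recovered after a 21-day delay is discontinued.

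**The concern.** The two sections give opposite instructions for the same event, and no text says which prevails. An investigator handling a Grade 4 event would naturally turn to the dose-modification section, and that section supplies a restart dose with no pointer to item 7. Table 10, the scale for events that CTCAE does not describe, labels Grade 4 life-threatening, so the question is whether to re-expose a patient after the most severe non-fatal grade.

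Part 2 plans about 20 centers, so the same event could be handled differently from one site to another. Safety is a primary endpoint, and Section 14.4.1 plans a summary of adverse events leading to discontinuation. That count would depend partly on which section a site followed. The stake is patient safety and consistent recording of discontinuations.

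**Working it through.** The plan gives no figure to reproduce here. The check is a comparison of text, plus one percentage.

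**Step 1: apply both rules to one patient.** Take a Part 2 patient on 280 mg with a first Grade 4 non-hematologic event, neither hepatic nor QTcF, that recovers within 21 days.

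| Source | Instruction |
|---|---|
| 7.4.3 item 7; synopsis item 7 | Withdraw |
| 6.1.4; Table 8 | Dosing ends once a 7.4.3 criterion is met |
| 8.5.2 general rule (Grade 3 or 4) | 240 mg on resuming |
| 8.5.2 diarrhea rule (Grade 3 or higher) | Hold, then may restart at 240 mg |
| 8.5.2 nausea/vomiting rule (Grade 3 or higher) | Hold, then may restart at 240 mg |

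The choice is between no drug and 240 mg. The reduction is (280 − 240)/280 = 40/280 = 14.3%.

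**Step 2: count the rules.** Section 8.5.2 has four restart rules after a first event: general, diarrhea, nausea/vomiting and liver enzymes. The first three reach Grade 4. The liver rule does not, because it restarts only after Grade 2 elevations and discontinues above 5 times ULN or on Hy's Law criteria. None of the three repeat-episode rules names Grade 4. If a Grade 4 restart were really intended, 8.5.2 would give no dose after a second Grade 4 event.

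**Step 3: look for a reconciling exception.** Item 4a is limited to progression, and the responder exception in item 8 and Section 8.5.3 is limited to QTcF. Neither reaches item 7. Section 8.5 does restate the 21-day limit (item 5), the liver criteria (item 6) and the QTcF criteria (item 8). Item 7 is the one dosing- or toxicity-based withdrawal criterion that it does not restate.

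**Step 4: narrow the overlap.**

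- *Hematologic events.* These fall outside the general rule. Grade 4 neutropenia lasting more than 5 days and Grade 4 thrombocytopenia enter 8.5.2 only through its Part 2 sentence on Table 6 toxicities, which asks only that a dose reduction be considered.
- *Liver events.* AST or ALT above 5 times ULN and Hy's Law cases are stopped in 8.5.2 itself, consistent with item 6.
- *QTcF events.* Those with a change above 60 ms or a value above 500 ms go to 8.5.3 and item 8.
- *Events without recovery in 21 days.* Both sections stop treatment.

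What remains in direct conflict is Grade 4 non-hematologic events that recover within 21 days and are not covered by the liver rule or 8.5.3.

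**The case against.** The strongest defense is that the protocol already ranks the two rules. Item 7 is mandatory, and 6.1.4 and Table 8 subject dosing to 7.4.3. Section 8.5.2 uses softer language: its general rule speaks conditionally of the dose on resuming, and the other two rules are optional. Section 2.4 reports no Grade 4 adverse events. Much of this stands: a careful reader would stop the drug, and no mishandled case is documented. But that reading leaves the Grade 4 wording in three restart rules with nothing to govern, and 8.5.2 does not send its user to item 7.

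A second defense is that item 7 may be the drafting error. It has no relatedness limit, so it withdraws patients even for unrelated Grade 4 events. The documents cannot exclude this, so the sponsor should confirm which rule is intended.

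Three stronger readings are tempting, and the documents do not support them.

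- A reader might infer that every Grade 4 event has a restart dose under 8.5.2. Step 4 of the working shows that the overlap is narrower.
- A reader might turn the zero Grade 4 count into a bound on how many remaining Part 2 patients are affected. That zero covers all Grade 4 events rather than the conflicting kind, pools doses from 40 to 320 mg, and does not make clear whether it refers to the 22 Part 1 patients or to all 34. An upper limit on a rate, multiplied by the patients still to enroll, is also not an upper bound on a patient count.
- A reader might conclude that all QTcF events should be taken out of the general rule. Section 8.5.3 acts only above 60 ms change or 500 ms. Grade 2 QTcF events below those triggers would then have no hold or reduction rule, although QTcF prolongation is the most common drug reaction reported under Section 2.4 (22 of 34 patients, three of them at Grade 2).

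**Conclusion.** The contradiction is real and stands in current text. For a Grade 4 non-hematologic event that recovers within 21 days and is not covered by the liver rule or Section 8.5.3, item 7 ends treatment and 8.5.2 offers 240 mg. Withdrawal is the better-supported reading; this rests on 6.1.4 and Table 8 making dosing subject to 7.4.3 and on item 7 appearing twice without qualification. The number of patients affected cannot be derived from the documents.

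This is an internal inconsistency in a safety rule that should be corrected at the next amendment. It bears on patient protection and on the count of discontinuations for adverse events. Nothing in the documents shows an effect on an efficacy estimate.

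**What to change.** In Section 8.5.2:

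1. Delete *or 4* from the general restart rule.
2. Change *grade ≥3* to *grade 3* in the diarrhea and nausea/vomiting restart rules.
3. Add: *Patients with a Grade 4 adverse event are withdrawn under Section 7.4.3 item 7 and are not restarted; this also applies to Grade 4 toxicities in Table 6. QTcF events that meet the Section 8.5.3 triggers are managed under that section.*

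The last sentence refers to the 8.5.3 triggers on purpose, so that Grade 2 QTcF events below them stay under the general rule.

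If the sponsor does intend recovered Grade 4 patients to restart, leave the three rules as they are. Qualify item 7 in both 7.4.3 and the synopsis (for example by relatedness, or by recovery within 21 days), and state the dose after a second Grade 4 event.

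The cost of the first option is three word-level edits and two added sentences. Neither option needs new assessments, data or analyses.
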